7.2 Record Retention

Records of the study (e.g., protocol, correspondence with Sponsor and IRB, IRB approvals, patient records, consents, and reports) must be maintained at least as long as local document retention regulations require.

7.3 Suspension and Termination

- Advanced Bionics reserves the right to terminate the study but intends only to exercise this right for valid scientific or business reasons and reasons related to protection of research subjects. The IRB will be notified in writing in the event of termination.
- Possible reasons for study termination include: The discovery of an unexpected, significant, or unacceptable risk to subjects enrolled in the study.

7.4 Investigator Responsibilities

The sponsor/investigator agrees to the following:

- Agree to sign and adhere to this protocol.
- Be willing to provide a signed a dated copy of the curriculum vitae including a statement of relevant experience including the dates, location, extent, and type of experience.
- Agree to disclose involvement in an investigation or other research that was terminated, and an explanation of the circumstances that led to termination.
- Agree to conduct the investigation in accordance with the investigational plan, all applicable FDA regulations, and conditions of approval imposed by the reviewing IRB.
- Supervise all testing involving human participants.
- Agree to obtain written informed consent before any study specific procedures are performed in accordance with GCP and that the requirements for obtaining informed consent are met.

8.0 World Medical Association Declaration of Helsinki

WORLD MEDICAL ASSOCIATION DECLARATION OF HELSINKI
Ethical Principles for Medical Research Involving Human Subjects

Adopted by the 18th WMA General Assembly, Helsinki, Finland, June 1964, and amended by the 29th WMA General Assembly, Tokyo, Japan, October 1975

Non-Significant Risk Study of a Cochlear Implant Headpiece

35th WMA General Assembly, Venice, Italy, October 1983

41st WMA General Assembly, Hong Kong, September 1989

48th WMA General Assembly, Somerset West, Republic of South Africa, October 1996

and the 52nd WMA General Assembly, Edinburgh, Scotland, October 2000

Note of Clarification on Paragraph 29 added by the WMA General Assembly, Washington 2002

Note of Clarification on Paragraph 30 added by the WMA General Assembly, Tokyo 2004

INTRODUCTION

The World Medical Association has developed the Declaration of Helsinki as a statement of ethical principles to provide guidance to physicians and other participants in medical research involving human subjects. Medical research involving human subjects includes research on identifiable human material or identifiable data.

It is the duty of the physician to promote and safeguard the health of the people. The physician's knowledge and conscience are dedicated to the fulfillment of this duty.

The Declaration of Geneva of the World Medical Association binds the physician with the words, "The health of my patient will be my first consideration," and the International Code of Medical Ethics declares that, "A physician shall act only in the patient's interest when providing medical care which might have the effect of weakening the physical and mental condition of the patient."

Medical progress is based on research which ultimately must rest in part on experimentation involving human subjects.

In medical research on human subjects, considerations related to the well-being of the human subject should take precedence over the interests of science and society.

The primary purpose of medical research involving human subjects is to improve prophylactic, diagnostic and therapeutic procedures and the understanding of the aetiology and pathogenesis of disease. Even the best proven prophylactic, diagnostic, and therapeutic methods must continuously be challenged through research for their effectiveness, efficiency, accessibility and quality.

In current medical practice and in medical research, most prophylactic, diagnostic and therapeutic procedures involve risks and burdens.

Medical research is subject to ethical standards that promote respect for all human beings and protect their health and rights. Some research populations are vulnerable and need special protection. The particular needs of the economically and medically disadvantaged must be recognized. Special attention is also required for those who cannot give or refuse consent for themselves, for those who may be subject to giving consent under duress, for those who will not benefit personally from the research and for those for whom the research is combined with care.

Research Investigators should be aware of the ethical, legal and regulatory requirements for research on human subjects in their own countries as well as applicable international

requirements. No national ethical, legal or regulatory requirement should be allowed to reduce or eliminate any of the protections for human subjects set forth in this Declaration.

9.0 Basic Principles for all Medical Research

It is the duty of the physician in medical research to protect the life, health, privacy, and dignity of the human subject.

Medical research involving human subjects must conform to generally accepted scientific principles, be based on a thorough knowledge of the scientific literature, other relevant sources of information, and on adequate laboratory and, where appropriate, animal experimentation.

Appropriate caution must be exercised in the conduct of research which may affect the environment, and the welfare of animals used for research must be respected.

The design and performance of each experimental procedure involving human subjects should be clearly formulated in an experimental protocol. This protocol should be submitted for consideration, comment, guidance, and where appropriate, approval to a specially appointed ethical review committee, which must be independent of the investigator, the sponsor or any other kind of undue influence. This independent committee should be in conformity with the laws and regulations of the country in which the research experiment is performed. The committee has the right to monitor ongoing trials. The researcher has the obligation to provide monitoring information to the committee, especially any serious adverse events. The researcher should also submit to the committee, for review, information regarding funding, sponsors, institutional affiliations, other potential conflicts of interest and incentives for subjects.

The research protocol should always contain a statement of the ethical considerations involved and should indicate that there is compliance with the principles enunciated in this Declaration.

Medical research involving human subjects should be conducted only by scientifically qualified persons and under the supervision of a clinically competent medical person. The responsibility for the human subject must always rest with a medically qualified person and never rest on the subject of the research, even though the subject has given consent.

Every medical research project involving human subjects should be preceded by careful assessment of predictable risks and burdens in comparison with foreseeable benefits to the subject or to others. This does not preclude the participation of healthy volunteers in medical research. The design of all studies should be publicly available.

Physicians should abstain from engaging in research projects involving human subjects unless they are confident that the risks involved have been adequately assessed and can be satisfactorily managed. Physicians should cease any investigation if the risks are found to outweigh the potential benefits or if there is conclusive proof of positive and beneficial results.

Medical research involving human subjects should only be conducted if the importance of the

Non-Significant Risk Study of a Cochlear Implant Headpiece

objective outweighs the inherent risks and burdens to the subject. This is especially important when the human subjects are healthy volunteers.

Medical research is only justified if there is a reasonable likelihood that the populations in which the research is carried out stand to benefit from the results of the research.

The subjects must be volunteers and informed participants in the research project.

The right of research subjects to safeguard their integrity must always be respected. Every precaution should be taken to respect the privacy of the subject, the confidentiality of the patient's information and to minimize the impact of the study on the subject's physical and mental integrity and on the personality of the subject.

In any research on human beings, each potential subject must be adequately informed of the aims, methods, sources of funding, any possible conflicts of interest, institutional affiliations of the researcher, the anticipated benefits and potential risks of the study and the discomfort it may entail. The subject should be informed of the right to abstain from participation in the study or to withdraw consent to participate at any time without reprisal. After ensuring that the subject has understood the information, the physician should then obtain the subject's freely-given informed consent, preferably in writing. If the consent cannot be obtained in writing, the non-written consent must be formally documented and witnessed.

When obtaining informed consent for the research project the physician should be particularly cautious if the subject is in a dependent relationship with the physician or may consent under duress. In that case the informed consent should be obtained by a well-informed physician who is not engaged in the investigation and who is completely independent of this relationship.

For a research subject who is legally incompetent, physically or mentally incapable of giving consent or is a legally incompetent minor, the investigator must obtain informed consent from the legally authorized representative in accordance with applicable law. These groups should not be included in research unless the research is necessary to promote the health of the population represented and this research cannot instead be performed on legally competent persons.

When a subject deemed legally incompetent, such as a minor child, is able to give assent to decisions about participation in research, the investigator must obtain that assent in addition to the consent of the legally authorized representative.

Research on individuals from whom it is not possible to obtain consent, including proxy or advance consent, should be done only if the physical/mental condition that prevents obtaining informed consent is a necessary characteristic of the research population. The specific reasons for involving research subjects with a condition that renders them unable to give informed consent should be stated in the experimental protocol for consideration and approval of the review committee. The protocol should state that consent to remain in the research should be obtained as soon as possible from the individual or a legally authorized surrogate.

investigators are obliged to preserve the accuracy of the results. Negative as well as positive results should be published or otherwise publicly available. Sources of funding, institutional affiliations and any possible conflicts of interest should be declared in the publication. Reports of experimentation not in accordance with the principles laid down in this Declaration should not be accepted for publication.

10.0 Additional Principles for Medical Research Combined with Medical Care

The physician may combine medical research with medical care, only to the extent that the research is justified by its potential prophylactic, diagnostic or therapeutic value. When medical research is combined with medical care, additional standards apply to protect the patients who are research subjects.

The benefits, risks, burdens and effectiveness of a new method should be tested against those of the best current prophylactic, diagnostic, and therapeutic methods. This does not exclude the use of placebo, or no treatment, in studies where no proven prophylactic, diagnostic or therapeutic method exists.⁴

At the conclusion of the study, every patient entered into the study should be assured of access to the best proven prophylactic, diagnostic and therapeutic methods identified by the study.⁵

⁴ The WMA hereby reaffirms its position that extreme care must be taken in making use of a placebo-controlled trial and that in general this methodology should only be used in the absence of existing proven therapy. However, a placebo-controlled trial may be ethically acceptable, even if proven therapy is available, under the following circumstances:

- Where for compelling and scientifically sound methodological reasons its use is necessary to determine the efficacy or safety of a prophylactic, diagnostic or therapeutic method; or
- Where a prophylactic, diagnostic or therapeutic method is being investigated for a minor condition and the patients who receive placebo will not be subject to any additional risk of serious or irreversible harm.

All other provisions of the Declaration of Helsinki must be adhered to, especially the need for appropriate ethical and scientific review.

⁵ The WMA hereby reaffirms its position that it is necessary during the study planning process to identify post-trial access by study participants to prophylactic, diagnostic and therapeutic procedures identified as beneficial in the study or access to other appropriate care. Post-trial access arrangements or other care must be described in the study protocol so the ethical review committee may consider such arrangements during its review.

Non-Significant Risk Study of a Cochlear Implant Headpiece

The physician should fully inform the patient which aspects of the care are related to the research. The refusal of a patient to participate in a study must never interfere with the patient-physician relationship.

In the treatment of a patient, where proven prophylactic, diagnostic and therapeutic methods do not exist or have been ineffective, the physician, with informed consent from the patient, must be free to use unproven or new prophylactic, diagnostic and therapeutic measures, if in the physician's judgment it offers hope of saving life, re-establishing health or alleviating suffering. Where possible, these measures should be made the object of research, designed to evaluate their safety and efficacy. In all cases, new information should be recorded and, where appropriate, published. The other relevant guidelines of this Declaration should be followed.

The Declaration of Helsinki (Document 17.C) is an official policy document of the World Medical Association, the global representative body for physicians. It was first adopted in 1964 (Helsinki, Finland) and revised in 1975 (Tokyo, Japan), 1983 (Venice, Italy), 1989 (Hong Kong), 1996 (Somerset-West, South Africa) and 2000 (Edinburgh, Scotland). Note of clarification on Paragraph 29 added by the WMA General Assembly, Washington 2002.

11.0 Appendix 2 Questionnaires

	Non-Significant Risk Study of a Cochlear Implant Headpiece Investigational Headpiece Baseline Questionnaire	[REDACTED] [REDACTED] [REDACTED] [REDACTED]
---	--	--

Subject ID: [REDACTED] - [REDACTED] Subject # - Subject initials (First, Middle, Last; if no middle initial, use a "-")	Visit Date: [REDACTED] Month [REDACTED] Day [REDACTED] Year
---	---

If you have any questions during the evaluation, please consult with the [REDACTED]
[REDACTED] [REDACTED]

Please indicate your rating:

1. Rate the retention of your personal headpiece				
Very Acceptable	Acceptable	No Opinion	Unacceptable	Very Unacceptable
				

2. Rate the comfort of your personal headpiece				
Very Acceptable	Acceptable	No Opinion	Unacceptable	Very Unacceptable
				

Thank you for your participation.

Non-Significant Risk Study of a Cochlear Implant Headpiece

Non-Significant Risk Study of a Cochlear Implant
Headpiece
Investigational Headpiece Fitting Form

Subject ID: -
Subject # - Subject initials
(First, Middle, Last; if no middle initial, use a "-")

Visit Date: -
 Month Day Year

To be completed by Study Staff:

Right Side	N/A 	Headpiece SN:
------------	---------------------------------	---------------

Left Side	N/A 	Headpiece SN:
-----------	---------------------------------	---------------

Study Staff (Print Name)	
Signature:	
Date:	

Non-Significant Risk Study of a Cochlear Implant Headpiece

	Non-Significant Risk Study of a Cochlear Implant Headpiece Investigational Headpiece Questionnaire	[REDACTED]
---	---	------------

Subject ID: [REDACTED] - [REDACTED] Subject # - Subject initials (First, Middle, Last; if no middle initial, use a "-")	Visit Date: [REDACTED] [REDACTED] - [REDACTED] [REDACTED] Month Day Year
---	---

Please refer to the following instructions during your time wearing the new headpiece.

1. Provide feedback on the headpiece and magnet configurations when requested.
2. If any headpiece discomfort arises during the study, please discontinue use of the investigational headpiece and resume use of your personal headpiece.
3. Return all investigational products to the Advanced Bionics Study Staff after the evaluation.

If you have any questions, please consult with the [REDACTED]

Date questionnaire was completed: [REDACTED]

[REDACTED]-[REDACTED]-[REDACTED][REDACTED]

Month Day Year

Please rate:

1. Is retention of the investigational headpiece acceptable?

Very Acceptable	Acceptable	No Opinion	Unacceptable	Very Unacceptable
				

2. Is comfort of the investigational headpiece acceptable?

Very Acceptable	Acceptable	No Opinion	Unacceptable	Very Unacceptable
				

Thank you for your participation.

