Primary Study Endpoint	Completion of all provided questionnaires that capture subjectively reported headpiece retention and comfort, as compared to baseline.
Primary Safety Endpoint	Cumulative frequency of adverse events and events per participant
Safety Parameters	Rate of adverse events
Control	Each participant will act as their own control
Research Hypothesis	The investigational headpiece and compatible magnets will provide participants with a retention option that is acceptable for daily use.
Study Schedule	Consent: Participants or will sign an informed consent form prior to the conduct of any study procedures. Baseline: Participants will complete a questionnaire regarding experience with their own headpiece at the time of consenting and enrollment. Follow up: Participants will evaluate the investigational headpiece during a chronic period of up to one-year or until the investigational headpiece receives FDA approval. They will complete questionnaires at two-month intervals. Off-Study: Participants will return their investigational headpieces to the Sponsor.
Experimental Hypothesis	A significant portion of study participants will report that the investigational headpiece is acceptable for wear during daily life.

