3.4 Description of all study procedures

The present study uses a single-group, prospective, within-subjects, repeated measures design, participants will complete questionnaires to provide subjectively reported opinions of investigational headpiece retention and comfort. Questionnaires will be available in English, French, and Spanish. English language examples are provided in Appendix 2.

Candidates for study participation and caregivers or family will be referred by audiologists from audiological and medical centers across the United States and Canada. The audiologist will be informed of this study by local Study Staff and the referral will be made through a telephone call, email, or in-person conversation. All participants will be recipients of commercially available Advanced Bionics' cochlear implants and the commercially available sound processors.

Study staff will contact prospective participants through a telephone call, email, or in-person conversation. A private location will be used for all study activities. Examples of private locations include but are not limited to: a meeting room in a hotel, a meeting room in an office building or clinic, or the participants home. Study staff will consent all participants prior to introduction of the cochlear implant headpiece. Participant contact information will be collected at this time, no other identifying or health-related information will be collected. If the participant is too young or unable to provide consent otherwise, a parent or guardian will complete the consenting process and the participant will be asked to assent to study participation.

Following completion of the informed consent, subjects will be asked to fill out a Baseline Questionnaire answering questions about their current headpiece. After completion of Baseline Questionnaire, Study staff will introduce the investigational headpiece and magnets to the participant. Participants and caregivers will have been previously trained and experienced in the use of their existing cochlear implant headpiece. Study staff will select the appropriate investigational headpiece magnet strength, identifying which magnet strength has appropriate retention. Appropriate retention is subjectively defined as retention sufficient to hold the headpiece in place during activities of daily life, while avoiding discomfort.

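### Baseline items use a neutral stem and investigational-headpiece items a stem naming the favourable answer, so wording changes exactly with device in the comparison to baseline (minor)

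*Protocol*

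**What the plan says.** Protocol section 11.0 (Appendix 2) prints two rating forms. The Baseline Questionnaire has two items, "Rate the retention of your personal headpiece" and "Rate the comfort of your personal headpiece". The Investigational Headpiece Questionnaire has two matching items, put as questions: "Is retention of the investigational headpiece acceptable" and "Is comfort of the investigational headpiece acceptable". Both forms offer the same five boxes in the same order, from very acceptable to very unacceptable, and both ask the respondent for a rating.

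Section 3.4 sets the order: "After completion of Baseline Questionnaire, Study staff will introduce the investigational headpiece and magnets to the participant". The baseline form therefore covers only the participant's own headpiece. The investigational form covers only the new one and is used at the initial visit and then every two months. Section 3.4 also says that the forms will exist in English, French and Spanish, and that Appendix 2 shows English examples.

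The Synopsis (section 1.0) gives the primary endpoint as "Completion of all provided questionnaires that capture subjectively reported headpiece retention and comfort, as compared to baseline" and the control as "Each participant will act as their own control". The experimental hypothesis is that "A significant portion of study participants will report that the investigational headpiece is acceptable for wear during daily life".

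**The concern.** A before-and-after comparison within participants is easiest to read when the measuring instrument stays the same and only the device changes. Here the instrument changes too, and at the same moment. The follow-up question puts the favourable answer into the stem; the baseline item does not. If that wording moves even a few respondents from one side of the scale to the other, the movement will be counted as a difference between headpieces.

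A single-group, open-label study already carries expectation and time effects that cannot be designed away. The stem is different: it could be matched by editing one line per item. The instruments are fixed in the protocol itself, so this is not a matter left to a statistical analysis plan. The protocol gives no reason for the different wording.

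**Working it through.** **Step 1. Set the forms side by side** (section 11.0).

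| Feature | Own headpiece (baseline) | Investigational headpiece |
|---|---|---|
| Retention stem | "Rate the retention of your personal headpiece" | "Is retention of the investigational headpiece acceptable" |
| Comfort stem | "Rate the comfort of your personal headpiece" | "Is comfort of the investigational headpiece acceptable" |
| Response labels | five, acceptability scale | the same five |
| Prompt to rate | yes | yes |
| Instruction block on wearing the new headpiece | no | yes |
| When used (section 3.4) | once, before the new headpiece is introduced | initial visit, then every two months |

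Two of two stems differ and five of five labels match.

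**Step 2. Is the wording effect identifiable?** Write the expected rating as a device effect plus a stem effect. Every own-headpiece rating has device = own and stem = neutral. Every investigational rating has device = new and stem = favourable pole named. The other two combinations never occur, so the change from baseline estimates only the sum of the two effects. No model or covariate can split that sum.

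**Step 3. What else differs in the same contrast?** Expectation and elapsed time differ. So does wear experience, since participants are used to their own headpiece and newly fitted with the other. Staff have newly selected the magnet strength (section 3.4), and the follow-up form carries the instruction block. Even in the first pair of forms, which section 3.4 appears to place at one visit, all of these except elapsed time still apply.

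**Step 4. Scale.** The protocol states no alpha, power, effect size or sample-size derivation, so there is no figure to reproduce. What follows is illustration. The only input from the documents is N = 20 to 200 (section 3.3). The assumptions are:

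- a share d = 10% to 30% of participants who cross between acceptable-or-better and not;
- a pure wording shift s of 0 to 5 percentage points;
- no device effect.

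With no net change, the 95% half-width for the paired change in proportion is 1.96 × √(d/N):

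- N = 20: 1.96 × √(0.10/20) = 13.9 points; 1.96 × √(0.30/20) = 24.0 points.
- N = 200: 1.96 × √(0.10/200) = 4.4 points; 1.96 × √(0.30/200) = 7.6 points.

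The shift s is added to the estimated change in full at any N. At s = 5 points it is well below random error at the minimum enrolment and similar to it at the maximum.

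As a further illustration, suppose a two-sided 5% McNemar test were used (the protocol names no test). Its normal approximation gives P(reject) = 1 − Φ[(1.96√(d/N) − s)/√((d − s²)/N)] + Φ[(−1.96√(d/N) − s)/√((d − s²)/N)]. With s = 5 points and d = 20%:

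- N = 20: 1 − Φ[(0.196 − 0.05)/0.0994] + Φ[(−0.196 − 0.05)/0.0994] = about 8%.
- N = 200: 1 − Φ[(0.0620 − 0.05)/0.0314] + Φ[(−0.0620 − 0.05)/0.0314] = about 35%.

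Over d = 10% to 30% the ranges are about 7% to 11% at N = 20 and 25% to 61% at N = 200. The approximation is crude at N = 20, where only 20 × 0.10 = 2 to 20 × 0.30 = 6 participants would be expected to change category. At s = 0 there is no bias. These figures show what an assumed shift would do; they are not evidence that a shift exists.

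**The case against.** The best defence is that little really changes. Both items are closed questions on the same acceptability scale, and both forms prompt for a rating, so a baseline respondent is also answering in terms of acceptability. The protocol states no test, margin or success threshold for the change from baseline. The primary endpoint is worded first as completion of questionnaires, and the follow-up stem asks directly what the experimental hypothesis is about. The size of any wording effect is wholly assumed, and the assumed range includes zero. All of this stands, and it is why the point is minor.

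It does not remove the point. The same endpoint sentence sets the ratings against baseline, the Synopsis makes each participant the control, and a matched stem on the same five boxes would answer the hypothesis just as well.

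Three stronger readings are tempting and are not supported:

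- A reader might infer that an open question becomes a closed one, or that the two sets of ratings cannot be compared. The identical labels and rating prompts rule that out.
- A reader might infer that wording is the only avoidable or the main difference, especially within the initial visit. Wear experience, magnet selection, expectation and the instruction block differ there as well.
- A reader might infer that the comparison is biased in favour of the new headpiece by a known amount. The documents establish neither direction nor size.

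It would also be too reassuring to say that the experimental hypothesis is untouched. It does not use the contrast with baseline, but if naming the favourable answer does shift responses, it could raise the stand-alone proportion who call the new headpiece acceptable.

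**Conclusion.** The point holds as a minor, avoidable weakness in the instruments. In the English example forms, stem and device change together for both items, so a wording effect and a device effect cannot be separated in the comparison to baseline. That conclusion follows from the text of the forms and the schedule and needs no assumption.

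The size does rest on assumptions. With a shift of at most 5 points and 10% to 30% of participants changing category, the bias would be hidden by random error near 20 participants and comparable with it near 200. Larger enrolment would not reduce it. The effect is probably small because the labels already impose an acceptability scale. Nothing can be said about the French and Spanish stems, which are not shown. Matching the stems would remove one source of bias; expectation, time and wear experience would remain.

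**What to change.** Use the baseline stem on the investigational form and change only the device name: *Rate the retention of the investigational headpiece* and *Rate the comfort of the investigational headpiece*, with the same five boxes. Check that the French and Spanish pairs of forms match in the same way. If forms with the current follow-up stem have already been returned, keep them, record the form version, and report the comparison to baseline separately by version.

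The cost is a short form revision with IRB approval; it adds no items, visits or staff time for participants' ratings. If the change is made during the study, some participants will have two wordings within their follow-up series, which is why the version must be recorded and reported.
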